2.1.3.2 Secondary efficacy endpoints

The secondary efficacy endpoints are:

- Change from Baseline to Week 26 in HbA1c (%) comparing sotagliflozin 200 mg versus placebo
- Comparison sotagliflozin 400 mg and 200 mg, respectively, versus placebo for:
 - Change from Baseline in FPG at Week 26

- Change from Baseline in body weight at Week 26
- Change from Baseline in SBP at Week 12 for patients with baseline SBP ≥ 130 mmHg
- Change from Baseline in SBP at Week 12 for all patients
- Change in the UACR (%) from Baseline to Week 26 for patients with a UACR >30 mg/g at baseline
- Proportion of patients with HbA1c $<6.5\%$, $<7.0\%$ at Week 26.

2.1.3.3 Other efficacy endpoints

- To compare sotagliflozin 400 mg and 200 mg versus placebo, respectively, in terms of:
 - Change from Baseline in SBP at Weeks 26 and 52 for patients with Baseline SBP ≥ 130 mmHg
 - Change from Baseline in SBP at Weeks 26 and 52 for all patients
 - Change from Baseline in HbA1c at Week 52
 - Change from Baseline in FPG at Week 52
 - Change from Baseline in body weight at Week 52
 - Change from Baseline in eGFR
 - Change from Baseline to Week 26 in:
 - Cystatin C
 - UGE
 - UGCR
 - Fructosamine
 - NT-proBNP
 - Proportion of patients with progression to end stage renal disease (ESRD) (dialysis or transplant) at Week 4 or any time later during the trial
 - Proportion of patients with $>50\%$ decline in eGFR from Baseline to Week 26 and Week 52
 - Proportion of patients with progression from normal to microalbuminuria or from microalbuminuria to macroalbuminuria from Baseline to Week 26 and Week 52
 - Proportion of patients with improvement from microalbuminuria to normal or from macroalbuminuria to microalbuminuria from Baseline to Week 26 and Week 52
 - Change from Baseline to Week 12 in SBP for patients with baseline SBP <130 mmHg
 - Change from Baseline to Week 12 in DBP for all patients and the subset of patients with baseline DBP ≥ 80 mmHg
 - Proportion of patients requiring rescue for hyperglycemia during 26-week double-blind period.

2.1.4 Safety endpoints

The safety analysis will be based on the reported adverse events, hypoglycemia, acute renal failure and other safety information, such as clinical laboratory data, vital signs, electrocardiogram (ECG), physical examination and marker of intestinal transit and absorption, markers of bone and calcium metabolism, etc.

Observation period

The observation period will be divided into 4 epochs:

- The **screening** epoch is defined as the time from the signed informed consent date up to the first administration of the double-blind IMP.
- The **treatment** epoch is defined as the time from the first administration of double-blind IMP to the last administration of double-blind IMP. This epoch includes the 26-week double-blind core treatment period and the 26-week double-blind extension treatment period. The 26-week core treatment period is the time from the first administration of double-blind IMP to the last administration of double-blind IMP on or before Visit 11 (Week 26) [or Day 182 if Visit 11 (Week 26) date is missing].
- The **residual treatment** epoch is defined as the time from the last administration of the IMP to the last administration of the IMP + 15 days (1 day for hypoglycemia).

The treatment-emergent adverse event (TEAE) period will include both **treatment** and **residual treatment** epochs (See the TEAE period for the 26-week core treatment period in [Section 2.5.4](#)).

- The **posttreatment** epoch is defined as the period of time starting the day after the end of the treatment-emergent adverse event period up to the last protocol-planned visit or the resolution/stabilization of all serious adverse events (SAE), adverse events of special interest (AESI) and events of special interest (EOSI), whichever is later.

The on-study observation period is defined as the time from start of double-blind treatment until the end of the study (defined as the last scheduled visit for those who completed the study and the date collected on e-CRF page “Completion of End of Study/Follow-up” for those who did not complete the study).

The post-study observation period is defined as the time from the day after the end of the study until the resolution/stabilization of all SAE, AESI and EOSI if applicable.

2.1.4.1 Hypoglycemia

Hypoglycemia will be identified as events recorded on the dedicated e-CRF “Hypoglycemic event information” page, and will be categorized as follows (see study protocol for further details):

Severe hypoglycemia

Severe hypoglycemia is an event requiring assistance of another person to actively administer carbohydrate, glucagon, intravenous glucose or other resuscitative actions. These episodes may be associated with sufficient neuroglycopenia to induce seizure, unconsciousness or coma.

Self-monitored plasma glucose values may not be available, but neurological recovery attributable to the restoration of plasma glucose to normal is considered sufficient evidence that the event was induced by a low plasma glucose concentration.

Severe hypoglycemia is identified in e-CRF “Hypoglycemic event information” page as those documented as,

To the question “Countermeasure Administration”, ticked the option “Subject was Not Capable of Treating Self and Required Assistance”, and

To the question “Were Symptoms Present”, ticked “Yes”.

Documented symptomatic hypoglycemia

Documented symptomatic hypoglycemia is an event during which typical symptoms of hypoglycemia accompanied by a measured plasma glucose concentration of ≤ 3.9 mmol/L (≤ 70 mg/dL).

Clinical symptoms that are considered to result from a hypoglycemic episode are eg, increased sweating, nervousness, asthenia/weakness, tremor, dizziness, increased appetite, palpitations, headache, sleep disorder, confusion, seizures, unconsciousness, or coma.

Documented symptomatic hypoglycemia is identified in e-CRF “Hypoglycemic event information” page as those documented as,

1. To the question “Countermeasure Administration”, NOT ticked the option “Subject was Not Capable of Treating Self and Required Assistance”, and
2. To the question “Were Symptoms Present”, ticked “Yes”, and
3. With a plasma glucose value before countermeasure ≤ 3.9 mmol/L (≤ 70 mg/dL).

Asymptomatic hypoglycemia

Asymptomatic hypoglycemia is an event not accompanied by typical symptoms of hypoglycemia but with a measured plasma glucose concentration ≤ 3.9 mmol/L (≤ 70 mg/dL).

Asymptomatic hypoglycemia is identified in e-CRF “Hypoglycemic event information” page as those documented as,

1. To the question “Countermeasure Administration”, NOT ticked the option “Subject was Not Capable of Treating Self and Required Assistance”, and
2. To the question “Were Symptoms Present”, ticked “No”, and
3. With a plasma glucose value before countermeasure ≤ 3.9 mmol/L (≤ 70 mg/dL).

Probable symptomatic hypoglycemia

Probable symptomatic hypoglycemia is an event during which symptoms of hypoglycemia are not accompanied by a plasma glucose determination, (but that was presumably caused by a plasma glucose concentration ≤ 3.9 mmol/L [≤ 70 mg/dL]), ie, symptoms treated with oral carbohydrate without a test of plasma glucose.

Probable symptomatic hypoglycemia is identified in e-CRF “Hypoglycemic event information” page as those documented as,

1. To the question “Countermeasure Administration”, NOT ticked the option “Subject was Not Capable of Treating Self and Required Assistance”, and
2. To the question “Were Symptoms Present”, ticked “Yes”, and
3. With no plasma glucose value before countermeasure, and
4. To the question “Did this countermeasure lead a significant improvement or prompt recovery?”, ticked “Yes”.

Relative hypoglycemia

Relative hypoglycemia, recently termed “pseudo-hypoglycemia” is an event during which the patient reports typical symptoms of hypoglycemia, and interprets the symptoms as indicative of hypoglycemia, but with a measured plasma glucose concentration > 3.9 mmol/L (> 70 mg/dL).

Relative hypoglycemia is identified in e-CRF “Hypoglycemic event information” page as those documented as,

1. To the question “Countermeasure Administration”, NOT ticked the option “Subject was Not Capable of Treating Self and Required Assistance”
2. To the question “Were Symptoms Present”, ticked “Yes”, and
3. With a plasma glucose value before countermeasure > 3.9 mmol/L (> 70 mg/dL).

In addition of the threshold of ≤ 3.9 mmol/L (≤ 70 mg/dL), hypoglycemia episodes with a plasma glucose of < 3.0 mmol/L (< 54 mg/dL) will be analyzed separately.

Any hypoglycemic event fulfilling the criteria of a SAE or leading to unconsciousness, coma, or seizure will also be recorded as a SAE (see [Section 2.1.4.2](#)).

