### Severe hypoglycemia

Severe hypoglycemia is an event requiring assistance of another person to actively administer carbohydrate, glucagon, intravenous glucose or other resuscitative actions. These episodes may be associated with sufficient neuroglycopenia to induce seizure, unconsciousness or coma. Self-monitored plasma glucose values may not be available, but neurological recovery attributable to the restoration of plasma glucose to normal is considered sufficient evidence that the event was induced by a low plasma glucose concentration.

**Note:** “Requiring assistance of another person” means that the patient could not help himself or herself to treat the hypoglycemia. Assisting a patient out of kindness, when assistance is not required, should not be considered a “requires assistance” incident.

Any hypoglycemic event which leads to unconsciousness, coma, or seizure should also be reported as an SAE.

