Chronic dialysis	(3) For dialysis, (3a) dialysis lasted for ≥ 90 days (e.g. end date – start date + 1 ≥ 90) as recorded in eCRF "Renal Event – Dialysis", OR (3b) positively adjudicated by CEC: Yes to the question ". Does the subject meet the criteria for ESRD".
Renal transplant	(4) "Renal transplant" captured in eCRF "Other procedure form", where adjudication is not required. PTs of Renal transplant (10038533), Renal and pancreas transplant (10052278), Renal and liver transplant (10052279) based on MedDRA v22.0.
Renal death	(5) Renal death as positively adjudicated by CEC: "Death - Non-Cardiovascular (Renal)" as the primary cause of death

EOSI not adjudicated*

Severe hypoglycemia	algorithm specified in Section 2.1.4.1 based on eCRF "Hypoglycemic Events"
Genital mycotic infections	PTs in Appendix C
Urinary tract infections	PTs in Appendix C,

AE Grouping	Criteria
Clinically relevant volume depletion and events related/possibly related to volume depletion	PTs in Appendix C
Diarrhea	Narrow search on “Noninfectious diarrhoea (SMQ)” [20000218] plus the following PTs (MedDRA v22.0): Gastroenteritis (10017888), Antidiarrhoeal supportive care (10055660), Enteritis (10014866), Enteritis leukopenic (10014877), Enterocolitis (10014893), Enterocolitis haemorrhagic (10014896)
Pancreatitis	PTs in Appendix C
Venous thrombotic events	PTs in Appendix C
Malignancies of special interest	Breast cancer: Narrow search on “Breast neoplasms, malignant and unspecified (SMQ)” [20000149] Prostate cancer: Narrow search on “Prostate neoplasms, malignant and unspecified (SMQ)” [20000152] Leydig-cell cancer: PTs of Leydig cell tumour of the testis (10024407) and Ovarian Sertoli-Leydig cell tumour (10073270) based on MedDRA v22.0 Thyroid cancer: PTs in Appendix C Renal cell cancer: PTs in Appendix C Pancreatic cancer: PTs in Appendix C Bladder cancer: PTs in Appendix C

EOSI AE leading to an amputation

Adverse event leading to an amputation	“AE Correction” as the reason for amputation in eCRF “Other Procedures related to Amputation”
AE potentially leading to an amputation *	PTs in Appendix C

* Search terms will be updated using the MedDRA version currently in effect at Sanofi at the time of database lock for EOSI identified by them. AE potentially leading to amputation: not one of EOSI defined in protocol, included and analyzed due to their relevance in regards to lower limb complications and amputations as a requirement from health authorities.

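### The SAP's severe-hypoglycemia rule adds a symptoms tick to the assistance criterion, so an assisted event without that tick falls in no category and leaves the severe count

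*SAP*

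**What the plan says.** **Written definition.** The SAP text in 2.1.4.1 reads: "Severe hypoglycemia is an event requiring assistance of another person to actively administer carbohydrate, glucagon, intravenous glucose or other resuscitative actions". Protocol 10.6.1 opens its definition with the same criterion, "Severe hypoglycemia is an event requiring assistance of another person to actively administer carbohydrate", and its note explains that requiring assistance "means that the patient could not help himself or herself to treat the hypoglycemia". Neuroglycopenia is described but not required: "These episodes may be associated with sufficient neuroglycopenia to induce seizure, unconsciousness or coma". The protocol's list of events of special interest (10.4.1.4) refers to 10.6.1 for severe hypoglycemia.

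**Algorithm.** SAP 2.1.4.1 then states how a severe event is found on the hypoglycemia e-CRF page. Two conditions are joined by an and: the countermeasure item has "ticked the option “Subject was Not Capable of Treating Self and Required Assistance”, and" the symptoms item is answered Yes ("To the question “Were Symptoms Present”, ticked “Yes").

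**Other categories.** Documented symptomatic, asymptomatic, probable symptomatic and relative hypoglycemia each begin with the opposite condition. The wording for the first two is "NOT ticked the option “Subject was Not Capable of Treating Self and Required Assistance”, and".

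**Use.** SAP Table 3 places severe hypoglycemia among the events of special interest that are not adjudicated and identifies it by this same algorithm. SAP 2.4.5.1 reports any, severe and documented symptomatic hypoglycemia as numbers and percentages of patients and as two incidence rates. It adds subgroup summaries and a Kaplan-Meier curve for severe or documented symptomatic events, and a listing of all recorded events with category flags.

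**The concern.** The derivation rule is narrower than the definition it is meant to implement. The e-CRF assistance option already records what the protocol's note describes, namely a patient who could not treat the episode unaided. The symptoms item is a second hurdle. If the two items disagree, the event fails the severe rule on the symptoms item and fails the other four on the assistance item.

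Severe hypoglycemia is a named safety outcome, and nothing later in the plan puts such an event back into it. Hypoglycemia is outside the endpoint committee's remit (protocol 6.3.3, SAP 2.1.4.2), and Table 3 relies on the same algorithm. The direction is also one-sided: the extra condition can remove a severe event but never add one. That differs from the SAP's handling of other incomplete safety data in 2.5.3, where an unclear onset date leads to classification as treatment-emergent and a missing causality assessment is taken as related.

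**Working it through.** The plan gives no figure to reproduce on this point. The check is one of logic.

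**Step 1. Conditions in SAP 2.1.4.1 side by side.**

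| Category | Assistance option | Symptoms item | Glucose before countermeasure | Recovery item |
|---|---|---|---|---|
| Severe | ticked | Yes | not used | not used |
| Documented symptomatic | not ticked | Yes | 3.9 mmol/L or below | not used |
| Asymptomatic | not ticked | No | 3.9 mmol/L or below | not used |
| Probable symptomatic | not ticked | Yes | none | Yes |
| Relative | not ticked | Yes | above 3.9 mmol/L | not used |

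The row that is absent is assistance ticked with symptoms not Yes.

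**Step 2. Enumeration of possible records.** Inputs: assistance (2 states), symptoms (Yes, No, blank: 3 states), glucose (at or below 3.9, above 3.9, none: 3 states), recovery (Yes or not: 2 states). The documents do not say whether the symptoms item can be left blank, so that state is an assumption.

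- All combinations: 2 × 3 × 3 × 2 = 36.
- Assisted: 1 × 3 × 3 × 2 = 18.
- Assisted with symptoms Yes: 1 × 1 × 3 × 2 = 6. All are severe.
- Assisted with symptoms No: 6. None has a category.
- Assisted with symptoms blank: 6. None has a category.

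So 12 of 18 assisted combinations are unclassified, whatever the glucose value, including values at or below 3.9 mmol/L. If the form does not allow a blank, the assisted combinations number 1 × 2 × 3 × 2 = 12, and 6 of these are unclassified. The No answer is a real option on the form, since the asymptomatic category depends on it. These are counts of combinations, not of expected events.

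**Step 3. The same enumeration with severe defined by the assistance tick alone.** All 18 assisted combinations are severe, none is unclassified, and no combination falls in two categories.

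**Step 4. Where an unclassified assisted event goes.**

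- Lost from: the severe number and percentage, both severe incidence rates, the subgroup summaries and Kaplan-Meier curve for severe or documented symptomatic events, and the severe-hypoglycemia event of special interest.
- Kept in: any hypoglycemia, on the natural reading that every event on the dedicated page counts; the listing, without a category flag; and serious adverse events, if it meets seriousness criteria or led to unconsciousness, coma or seizure.

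**Step 5. Size, by illustration only.** The planned number per arm is 92 (protocol 11.1). The numbers of severe cases below are assumed. One patient is 1/92 = 1.1 percentage points. If one patient's only severe event is unclassified:

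- 1 affected patient: 1/92 = 1.1% becomes 0%.
- 3 affected patients: 3/92 = 3.3% becomes 2/92 = 2.2%, a fall of one third.
- 5 affected patients: 5/92 = 5.4% becomes 4/92 = 4.3%, a fall of one fifth.

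The documents give neither the number of severe events nor the frequency of disagreement between the two items.

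**The case against.** **Assisted events have symptoms, so the condition is harmless.** This is the strongest reply, and much of it stands. Protocol 10.6.1 and SAP 2.1.4.1 list confusion, seizures, unconsciousness and coma among the symptoms of hypoglycemia, and the e-CRF page collects signs as well as symptoms. The footnote to protocol Figure 1 attributes the inability to self-treat to acute neurological impairment, which implies symptoms. The symptoms condition is therefore not wholly foreign to the protocol. The figure itself is not reproduced in the text available, so the order of its branches cannot be checked. But if symptoms are always implied, the condition does nothing on a correct form and acts only on an inconsistent or incomplete one, where it discards the event.

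**A stronger reading to avoid.** A reader might infer that the gravest events, such as a patient found unconscious and unable to report anything, are the ones most likely to be lost. The documents do not support this. Unconsciousness counts as a symptom, so a properly completed form would say Yes and the event would be severe. A reader might also infer that affected events vanish from safety reporting. They do not, as Step 4 shows.

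**The condition may screen out false severe events.** A carer-dependent patient with a low reading and no symptoms might be given carbohydrate and recorded as assisted. Dropping the symptoms condition without any check could count that as severe. The point is fair. The protocol's note already excludes help that was not needed, so such a record is a wrong assistance tick, best corrected by query.

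**Queries already exist, and safety analyses are descriptive.** Protocol 13.4 obliges the investigator to answer data queries, but this check is not named. That no significance test depends on the count limits the consequence. It does not make the count right.

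**Conclusion.** The point holds as a narrow defect in a derivation rule. SAP 2.1.4.1 asks for more than the written definitions do, and only the Figure 1 footnote implies the extra condition. An assisted event with symptoms answered No falls in none of the five categories and leaves every severe-hypoglycemia summary. The same is true of a blank answer if the form permits one.

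The practical size is probably small and cannot be estimated from the documents. The records at risk are mainly those where the two e-CRF items disagree through data entry. What makes it worth correcting is that the error runs one way only, towards under-reporting a named safety outcome. Severe events may also be few, in which case a single record would move an arm's percentage visibly.

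**What to change.** In SAP 2.1.4.1, classify as severe every event with the assistance option ticked, whatever the symptoms item says. Table 3 follows automatically because it refers to that section. Record the change in the SAP's own table of statistical changes.

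Add a data check: every assisted record without symptoms answered Yes is queried with the site before the final database lock, by staff without access to treatment codes. SAP 1.6 records that the first-step analysis has already been run, so the separation of unblinded staff described in SAP section 3 must cover this check. A wrongly ticked assistance option is then corrected at source, and a missing or mistaken symptoms answer is completed.

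The cost is one condition removed from the program, one data check, and possibly a slightly higher severe count. No other category changes: on the enumeration above, no record falls in two categories.

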2.1.4.2 Adverse events variables***Adverse event observation period***

- Pretreatment adverse events are adverse events that developed or worsened or became serious from the signed informed consent date up to first administration of double-blind IMP
- Treatment-emergent adverse events are adverse events that developed or worsened or became serious during the treatment-emergent adverse event period
- Posttreatment adverse events are adverse events that developed or worsened or became serious during the posttreatment period

All adverse events (including SAE, AESI and EOSI) will be coded to a lower-level term (LLT), preferred term (PT), high-level term (HLT), high-level group term (HLGT), and associated primary system organ class (SOC) using the version of MedDRA currently in effect at Sanofi at the time of database lock.

The occurrence of adverse events (including SAE, AESI and EOSI) will be recorded from the time of signed informed consent until the end of the study (see [Section 2.1.4](#)) or the resolution/stabilization of all SAE, AESI and EOSI.

AESI include:

- Pregnancy
- Symptomatic overdose with IMP/NIMP
- Alanine aminotransferase (ALT) increase > 3 times upper limit of normal (ULN)

EOSI include:

- Major adverse cardiovascular events (MACE [cardiovascular death, myocardial infarction, or stroke]) and other specific cardiovascular (CV) events (eg, heart failure requiring hospitalization)
- Severe hypoglycemia
- Genital mycotic infections (to include vulvovaginal candidiasis in females and candida balanitis in males)
- Urinary tract infection
- Clinically relevant volume depletion and events related/possibly related to volume depletion
- Diarrhea
- Pancreatitis
- Bone fractures

- Venous thrombotic events, to include deep venous thrombosis and thromboembolism (to include pulmonary embolism)
- Diabetic ketoacidosis
- Renal events, to include 50% decline in eGFR, end stage kidney disease, renal death
- Malignancies of special interest (breast, bladder, renal cell, Leydig cell, pancreatic, prostate, and thyroid cancer)
- Adverse event leading to an amputation

The Clinical Endpoint Committee (CEC) will, in a blinded manner, review and adjudicate all deaths, myocardial infarction, stroke, unstable angina requiring hospitalization, and heart failure requiring hospitalization, selected renal events, bone fracture, and DKA.

Two independent committees will review safety events that require ongoing monitoring to ensure timing protocol amendments in case a safety signal is identified. These events are: 1) potential cases of drug-induced liver injury (DILI), and 2) cases of amputations. The two committees will review the cases in a treatment-blinded manner and will present their assessment to the DMC.

AESI and EOSI will be identified based on criteria in Table 3.

Table 3 - Criteria for AESI and EOSI

AE Grouping	Criteria
AESI	
Pregnancy	eCRF "Pregnancy"
Symptomatic overdose with IMP/NIMP	"Overdose of IMP" or "Overdose of NIMP" checked and "Symptomatic overdose" checked in eCRF "Overdose"
ALT increase > 3X ULN	eCRF "ALT increase"
EOSI adjudicated	
Cardiovascular death	Positively adjudicated by CEC: "Cardiovascular" or "Undetermined" as the primary cause of death
Myocardial infarction, Unstable Angina requiring hospitalization	Positively adjudicated by CEC: Yes to the question "Does the event meet the definition of an MI for this study?", or Yes to the question "If event is not an MI, does the event meet the definition of an UA Requiring admission to hospital or emergency room, for this study?"
Stroke	Positively adjudicated by CEC: Yes to the question "Does the event meet the definition of a Stroke for this study?"
Heart failure requiring hospitalization	Positively adjudicated by CEC: Yes to the question "Does the event meet the definition of a Heart Failure Event for this study?"

AE Grouping	Criteria
Bone fractures	Positively adjudicated by CEC: Yes to the question "Did the Fracture occur?"
Diabetic ketoacidosis	Positively adjudicated by CEC: Yes to the question "Does this event meet the criteria to be a DKA event?"

EOSI Renal events where select events adjudicated

Sustained $\geq 50\%$ decrease in eGFR	(1) For $\geq 50\%$ decrease in eGFR from baseline, (1a) confirmed $\geq 50\%$ decrease in GFR for ≥ 30 days with no reversible cause as recorded in eCRF "eGFR decrease", OR (1b) positively adjudicated by CEC: Yes to the question "Does the subject meet the criteria of CKD progression".
Sustained eGFR < 15 mL/min/1.73 m ²	(2) For eGFR < 15 mL/min/1.73 m ² , (2a) confirmed eGFR < 15 mL/min/1.73 m ² for ≥ 30 days with no reversible cause as recorded in eCRF "eGFR decrease", OR (2b) positively adjudicated by CEC: Yes to the question "Does the subject meet the criteria of CKD progression".
Chronic dialysis	(3) For dialysis, (3a) dialysis lasted for ≥ 90 days (e.g. end date – start date + 1 ≥ 90) as recorded in eCRF "Renal Event – Dialysis", OR (3b) positively adjudicated by CEC: Yes to the question ". Does the subject meet the criteria for ESRD".
Renal transplant	(4) "Renal transplant" captured in eCRF "Other procedure form", where adjudication is not required. PTs of Renal transplant (10038533), Renal and pancreas transplant (10052278), Renal and liver transplant (10052279) based on MedDRA v22.0.
Renal death	(5) Renal death as positively adjudicated by CEC: "Death - Non-Cardiovascular (Renal)" as the primary cause of death

EOSI not adjudicated*

Severe hypoglycemia	algorithm specified in Section 2.1.4.1 based on eCRF "Hypoglycemic Events"
Genital mycotic infections	PTs in Appendix C
Urinary tract infections	PTs in Appendix C,

AE Grouping	Criteria
Clinically relevant volume depletion and events related/possibly related to volume depletion	PTs in Appendix C
Diarrhea	Narrow search on “Noninfectious diarrhoea (SMQ)” [20000218] plus the following PTs (MedDRA v22.0): Gastroenteritis (10017888), Antidiarrhoeal supportive care (10055660), Enteritis (10014866), Enteritis leukopenic (10014877), Enterocolitis (10014893), Enterocolitis haemorrhagic (10014896)
Pancreatitis	PTs in Appendix C
Venous thrombotic events	PTs in Appendix C
Malignancies of special interest	Breast cancer: Narrow search on “Breast neoplasms, malignant and unspecified (SMQ)” [20000149] Prostate cancer: Narrow search on “Prostate neoplasms, malignant and unspecified (SMQ)” [20000152] Leydig-cell cancer: PTs of Leydig cell tumour of the testis (10024407) and Ovarian Sertoli-Leydig cell tumour (10073270) based on MedDRA v22.0 Thyroid cancer: PTs in Appendix C Renal cell cancer: PTs in Appendix C Pancreatic cancer: PTs in Appendix C Bladder cancer: PTs in Appendix C

EOSI AE leading to an amputation

Adverse event leading to an amputation	“AE Correction” as the reason for amputation in eCRF “Other Procedures related to Amputation”
AE potentially leading to an amputation *	PTs in Appendix C

* Search terms will be updated using the MedDRA version currently in effect at Sanofi at the time of database lock for EOSI identified by them. AE potentially leading to amputation: not one of EOSI defined in protocol, included and analyzed due to their relevance in regards to lower limb complications and amputations as a requirement from health authorities.

